#### **4.2.2. Pediatric Subjects**

21. Subject has moderate or severe illness (this does not include minor illnesses such as diarrhea) or temperature  $\geq 38.0$  °C/100.4 °F within 24 hours prior to the first dose of study vaccine; enrollment at a later date is permitted.

- 
22. Subject's weight is below 10th percentile according to World Health Organization (WHO) pediatric growth and weight charts.
  23. Criterion amended per Amendment 3:
    - 23.1 Subject has any clinically significant acute or chronic medical condition that, in the opinion of the investigator, would preclude participation: eg, history of seizure disorders, bleeding/clotting disorder, autoimmune disease, active malignancy, systemic infections, congenital heart disease, history of any pulmonary condition requiring medication, atopy, reactive airway disease, medically-confirmed wheezing, bronchoconstriction or treatment with a  $\beta$ 2 agonist, cystic fibrosis, bronchopulmonary dysplasia, chronic pulmonary disease, medically-confirmed apnea, hospitalization for respiratory illness, or mechanical ventilation for respiratory illness.
  24. Subject has major congenital anomalies or known cytogenetic disorders (eg, Down's syndrome).
  25. Subject has had major surgery within the 4 weeks prior to randomization or has planned major surgery through the course of the study.
  26. Subject is in receipt of, or planning to receive, live attenuated vaccine (eg, measles, mumps and rubella [MMR] or varicella, but excluding rotavirus vaccine) within 28 days of each study vaccination (ie, before and after); other vaccines (eg, influenza, pertussis, polio or rotavirus) should be given at least 14 days before or 14 days after each study vaccination. *Note:* Planning for routine childhood vaccinations will be available from the site to ensure that these can be taken at appropriate times during the study.
  27. Subject has known or suspected immunodeficiency, such as known HIV infection.
  28. Subject has received an investigational drug or used an invasive investigational medical device within 30 days or received an investigational vaccine within 6 months before the planned administration of the first dose of study vaccine or is currently enrolled or plans to participate in another investigational study during the course of this study. *Note:* *Participation in an observational clinical study (ie, with no intervention) is allowed upon approval of the sponsor.*
  29. Criterion amended per Amendment 3:
    - 29.1 Subject has a known allergy to vaccines or vaccine components (including any of the constituents of the study vaccine), or history of anaphylaxis or other serious adverse reactions to vaccines or vaccine components (including any of the constituents of the study vaccine). *Note:* subjects with egg allergies can be enrolled.
  30. Criterion amended per Amendment 3:
    - 30.1 Subject has a history of the following moderate to severe chronic conditions: urticaria (recurrent hives), eczema and/or atopic dermatitis.
  31. Subject has a history of acute polyneuropathy (eg, Guillain-Barré syndrome).
-

32. Subject has chronic or recurrent use of immunomodulators/suppressors, eg, cancer chemotherapeutic agents, oral or parenteral corticosteroids for at least 5 days within 42 days prior to randomization, or planned during the course of the study.
33. Subject has a history of receipt of blood products or Ig within 3 months of randomization. Subject has been in receipt of palivizumab/Synagis® or received any other vaccine or monoclonal/polyclonal antibody in a previous RSV study at any time prior to randomization.
34. Subject has a contraindication to intramuscular injections and blood draws, eg, bleeding disorders.
35. Subject has a history of an underlying clinically significant acute or chronic medical condition or physical examination findings for which, in the opinion of the investigator, participation would not be in the best interest of the subject (eg, compromise the well-being) or that could prevent, limit, or confound the protocol-specified assessments.
36. Subject's parent(s)/legal guardian(s) cannot communicate reliably with the investigator.
37. Subject is a family member of either the investigator, study-site employee, or employee of the sponsor.

*Note:* Investigators should ensure that all study enrollment criteria have been met at screening. If a subject's clinical status changes (including any available laboratory results or receipt of additional medical records) after screening but before the first dose of study vaccine is given such that he or she no longer meets all eligibility criteria, then the subject should be excluded from participation in the study. Section 17.4, Source Documentation, describes the required documentation to support meeting the enrollment criteria.

### **4.3. Prohibitions and Restrictions**

Potential subjects must be willing and able to adhere to the following prohibitions and restrictions during the course of the study to be eligible for participation:

1. Refer to Section 8, for details regarding prohibited and restricted therapy during the study.
2. Agree to follow all requirements that must be met during the study as noted in the inclusion and exclusion criteria (Section 4.1.1 and Section 4.2.1, respectively, for adult subjects, and Section 4.1.2 and Section 4.2.2, respectively, for pediatric subjects).
3. Vaccination with live attenuated vaccines within 28 days of a study vaccination (ie, before and after) is prohibited. Other vaccines (eg, influenza, tetanus, hepatitis A, hepatitis B, rabies) should be given at least 14 days before (or at least 14 days after) administration of study vaccine in order to avoid potential confusion of adverse reactions and potential immune interference. If a vaccine is indicated in a post-exposure setting (eg, rabies or tetanus), it must take priority over the study vaccine.
4. *Cohort 1 only:* Subjects should receive all routine immunizations according to applicable national guidelines. A subject will not postpone, forego or delay the receipt of any recommended vaccine according to local schedules (eg, in Europe, the applicable national

immunization schedules, and the equivalent in other countries) due to participation in the current study. All subjects should receive routine immunizations according to schedule.

## **5. STUDY VACCINE ALLOCATION AND BLINDING**

### **Study Vaccine Allocation**

Central randomization will be implemented in this study. Within each cohort, subjects will be randomly assigned to one of the two groups based on a computer-generated randomization schedule prepared before the study by or under the supervision of the sponsor. The randomization will be balanced by using randomly permuted blocks. Initially 2 sentinel subjects (one Ad26.RSV.preF and one placebo) will be enrolled to monitor for any unexpected severe adverse reaction to the vaccine. Therefore, the randomization of the first block will be phased to accommodate this. The remainder of the blocks will be filled to have an overall 2:1 randomization ratio. No stratification will be applied. The interactive web response system (IWRS) will assign a unique code, which will dictate the group assignment for the subject. The requestor must use his or her own user identification and personal identification number when contacting the IWRS, and will then give the relevant subject details to uniquely identify the subject.

If randomized subjects are withdrawn from vaccination before the first dose is administered, additional subjects may be recruited to replace these subjects at the discretion of the sponsor. Any replacement subject will be assigned to the same group as the original (discontinued) subject. The replacement subject's randomization number will equal the randomization number of the discontinued subject +1000 (for example subject 0001 would be replaced by subject 1001). These additional subjects should also be randomized through IWRS.

Any randomized subject who is withdrawn from the study for reasons other than due to an AE after the first dose but before the second dose might be replaced at the discretion of the sponsor. Any replacement subject will be assigned to the same group as the original (discontinued) subject. The replacement subject's randomization number will equal the randomization number of the discontinued subject +2000.

### **Blinding**

The investigator will not be provided with randomization codes until the final analysis is performed. The codes will be maintained within the IWRS, which has the functionality to allow the investigator to break the blind for an individual subject.

Unblinding (ie, at the subject level) will only occur at the time of database lock of the final analysis. While the responsibility to break the study vaccine allocation code in emergency situations resides solely with the investigator, it is recommended that the investigator contact the sponsor or its designee to discuss the particular situation, before breaking the blind. Telephone contact with the sponsor or its designee will be available 24 hours per day, 7 days per week. In such cases, the investigator may in an emergency determine the identity of the study vaccine by contacting the IWRS. In the event the blind is broken, the sponsor must be informed as soon as

possible. The date, time and reason for the unblinding must be documented by the IWRS, in the appropriate section of the electronic case report form (eCRF), and in the source document. The documentation received from the IWRS indicating the code break must be retained with the subject's source documents in a secure manner.

The subjects, study-site personnel, and investigator, and sponsor personnel will be blinded to study vaccine allocation throughout the study, except for the pharmacist or qualified staff member with primary responsibility for study vaccine preparation and dispensing. The pharmacy and preparation of study vaccines will be monitored by an independent study vaccine monitor (see Section 17.8).

*Note:* the unblinded pharmacist, or other qualified individual, may also perform the vaccine administration, but will have no other study function from randomization onwards.

The primary analysis, and any other interim analysis performed before the final analysis, will be performed on data unblinded at the group levela; there will be no unblinding at the subject level. These data will only be available to a selected group of sponsor personnel, excluding sponsor personnel involved in data collection or data management.

In general, randomization codes will be disclosed fully only if the study is completed and the clinical database is closed.

If the randomization code is broken by the investigator or the study-site personnel, the subject must discontinue further study vaccine administration and must be followed as appropriate (see Section 10.2 for details). If the randomization code is broken by the sponsor for safety reporting purposes, the subject should not discontinue further study vaccine administration and may remain in the study (if the randomization code is still blinded to the study-site personnel and the subject).

## **6. DOSAGE AND ADMINISTRATION**

Ad26.RSV.preF (JNJ-64400141) will be supplied in single-use vials. Volumes of 0.5 mL ( $1 \times 10^{11}$  vp) for adults and 0.25 mL ( $5 \times 10^{10}$  vp) for toddlers will be used for intramuscular injection.

Placebo will be supplied as sterile 0.9% saline for injection.

An unblinded pharmacist, or other qualified individual will prepare the appropriate vial and syringe and provide the syringe in a blinded manner to the study vaccine administrator who will perform the injection.

---

a To preserve the blind at the subject level, dummy subject identification numbers will be used to link the data to the randomization codes. The results of this analysis will only be distributed to sponsor personnel not directly involved in data collection and data management.

*Note:* the unblinded pharmacist, or other qualified individual, may also perform the administration, but will have no other study function from randomization onwards.

Further details on study vaccine preparation will be provided in the Investigational Product Preparation Instructions.

For adult subjects, injections should be administered in the deltoid. For pediatric subjects, injections should be administered in the anterolateral aspect of the thigh. Alternating injection sites will be used for the vaccinations on Day 1 and Day 29.

## **7. STUDY VACCINE COMPLIANCE**

Study vaccine will be administered intramuscularly by a study vaccine administrator – a trained and qualified study nurse, medical doctor, or otherwise qualified health care professional. The date and time of each study vaccine administration will be recorded in the eCRF.

## **8. PRE-STUDY AND CONCOMITANT THERAPY**

Pre-study therapies administered up to 30 days before the first dose of study vaccine must be recorded in the eCRF during screening.

Concomitant therapies will be collected and recorded in the eCRF from time of each vaccine administration through 28 days after each vaccination, and additionally outside of these periods when associated with an SAE meeting the criteria outlined in Section 12.3.2. Information on concomitant use of herbal supplements or vitamins will not be collected.

Use of any experimental medication (including experimental vaccines other than the study vaccine) during the study is not allowed.

Subjects can receive medications such as acetaminophen, non-steroidal anti-inflammatory drugs (NSAIDs), or antihistamines as needed, although their use must be documented and use of these medications as routine prophylaxis prior to study vaccination is discouraged, unless if specified by the sponsor. (*Note:* The use of EMLA® Cream [2.5% lidocaine and 2.5% prilocaine] as a topical anesthetic will not be prohibited during the study.)

*For adult subjects:* chronic (longer than 10 days) or recurrent use of systemic corticosteroids is prohibited during the study and within 6 months before first administration of study vaccine (*Note:* ocular, topical or inhaled steroids are allowed). Antineoplastic and immunomodulating agents or radiotherapy are prohibited in the 6 months prior to screening and during the study.

*For pediatric subjects:* chronic or recurrent use of immunomodulators/suppressors, eg, cancer chemotherapeutic agents, oral or parenteral corticosteroids for at least 5 days within 42 days prior to randomization, or planned during the course of the study.

If chronic use of prohibited therapies becomes medically indicated during the course of the study for any subject, the sponsor should be contacted.

Vaccination with live attenuated vaccines within 28 days of a study vaccination (ie, before and after) is prohibited. Other licensed vaccines (ie, not live) should be given at least 14 days before or at least 14 days after administration of study vaccine in order to avoid potential confusion of adverse reactions and potential immune interference. If a vaccine is indicated in a post-exposure setting (eg, rabies or tetanus), it must take priority over the study vaccine.

*For pediatric subjects:* planning for routine childhood vaccinations will be available from the site to ensure that these can be taken at appropriate times during the study.

The sponsor must be notified in advance (or as soon as possible thereafter) of any instances in which prohibited therapies are administered.

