10. Subject has received an investigational drug or used an invasive investigational medical device within 30 days or received an investigational vaccine within 6 months before the planned administration of the first dose of study vaccine or is currently enrolled or plans to participate in another investigational study during the course of this study. *Note: Participation in an observational clinical study (ie, with no intervention) is allowed upon approval of the sponsor.*
  11. Subject has received treatment with Ig in the 2 months, or blood products in the 4 months before the planned administration of the first dose of study vaccine or has any plans to receive such treatment during the study.
  12. Subject has a known allergy, or history of anaphylaxis or other serious adverse reactions to vaccines or vaccine components (including any of the constituents of the study vaccine).
  13. Subject has a history of chronic urticaria (recurrent hives), eczema and/or atopic dermatitis.
  14. Subject has a history of acute polyneuropathy (eg, Guillain-Barré syndrome).
  15. Subject has abnormal function of the immune system resulting from:
    - Clinical conditions (eg, autoimmune disease or immunodeficiency)
    - Chronic (longer than 10 days) or recurrent use of systemic corticosteroids during the study and within 6 months before first administration of study vaccine (*Note: ocular, topical or inhaled steroids are allowed*)
    - Administration of antineoplastic and immunomodulating agents or radiotherapy during the study and within 6 months before first administration of study vaccine
  16. Subject has a contraindication to intramuscular injections and blood draws, eg, bleeding disorders.
  17. Subject is a woman who is pregnant, or breast-feeding, or planning to become pregnant while enrolled in this study or within 3 months after the last dose of study vaccine.
  18. Subject is an employee of the investigator or study site, with direct involvement in the proposed study or other studies under the direction of that investigator or study site, as well as family members of the employees or the investigator, or an employee of the sponsor.
  19. Subject cannot communicate reliably with the investigator.
  20. Subject who, in the opinion of the investigator, is unlikely to adhere to the requirements of the study, or are unlikely to complete the full course of vaccination and observation.

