**Post-second Vaccination: Visits 6, 7, 8 and 9 (3, 7 and 28 Days and 6 Months Post-second Vaccination)**

**Visit 6** at 3 days post-vaccination will be a telephone call to check subject diaries and to collect safety information (solicited and unsolicited AEs, SAEs and concomitant medications).

**Visit 7** at 7 days after the second vaccination will include an abbreviated physical examination (at the discretion of the investigator), vital signs measurement, and recording of any AEs/SAEs, concomitant medications and RTIs. The subject diary will be reviewed and collected. If Visit 7 occurs before the end of the diary period after the second vaccination, review of the diary will still take place, but the diary will be returned by the subject's parent/guardian or caregiver at Visit 8.

**Visit 8** at 28 days after the second vaccination will include an abbreviated physical examination (at the discretion of the investigator), vital signs measurement (at the discretion of the investigator), measurement of body height and weight, recording of any unsolicited AEs/SAEs, concomitant medications, and RTIs. Blood samples will be collected for immunogenicity assessments.

**Visit 9** at 6 months after the second vaccination will include an abbreviated physical examination (at the discretion of the investigator), vital signs measurement (at the discretion of the investigator), measurement of body height and weight, recording of any SAEs and associated concomitant medications, and RTIs. Blood samples will be collected for immunogenicity assessments. Visit 9 (Day 211) will be the final visit of the active phase for Cohort 1 subjects. *Note:* If Visit 9 occurs during the RSV season, an additional visit will be made by telephone at the end of the RSV season to collect safety information.

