### 11.1. Analysis Sets

The **Full Analysis Set (FA)** includes all subjects who were randomized and received at least one dose of study vaccine, regardless of the occurrence of protocol deviations. Vaccination assignment will follow the as-treated principle. All safety analyses will be based on the FA set. As a sensitivity analysis, key immunogenicity tables will also be based on the FA set.

The **Per-protocol Immunogenicity Set (PPI)** will include all randomized and vaccinated subjects for whom immunogenicity data are available, excluding subjects with major protocol deviations expected to impact the immunogenicity outcomes.

In addition, the following samples will not be included in the PPI set:

- If subjects miss one or more doses, but continue the planned visit schedule, samples taken after the planned but missed dose(s) will not be taken into account;
- For subjects who experience a natural RSV infection (based on RT-PCR, or other sources), samples taken after the natural infection are not be taken into account.
- Any subject who receives study vaccine beyond the Day 29 window specified in the Time and Events Schedule would not be included in the per-protocol immunogenicity analyses.

The analysis of immunogenicity will be based on the PPI set.

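### Immunoglobulin, blood product or RSV antibody given to a toddler in-study breaks no written rule, has no per-protocol exclusion, and without an SAE is not recorded after about Day 57, although Day 211 is a per-protocol immunogenicity time point

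*Protocol*

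**What the plan says.** **Recording window.** Protocol Section 8 says that "Concomitant therapies will be collected and recorded in the eCRF from time of each vaccine administration through 28 days after each vaccination". The only extension to other times is for therapy tied to an SAE. Schedule note s says the same. At Visit 9 (Day 211, Section 9.1.4.2.3) the site's task is "recording of any SAEs and associated concomitant medications, and RTIs", so medication is asked about only where an SAE is involved. Adult Visit 8 is worded similarly.

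**Toddler rule.** Criterion 33 in Section 4.2.2 begins "Subject has a history of receipt of blood products or Ig within 3 months of randomization" and goes on to palivizumab and to RSV vaccines or antibodies from earlier studies, again only before randomization. The criteria re-checked before each toddler dose are 21, 22, 25, 26, 28 and 32. The Section 8 text for pediatric subjects mentions immunomodulators and suppressors but not these products.

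**Adult rule.** Criterion 11 in Section 4.2.1 covers past immunoglobulin and blood products and adds "or has any plans to receive such treatment during the study". It is on the adult re-check list.

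**Analysis set.** Protocol 11.1 defines the PPI set by "excluding subjects with major protocol deviations expected to impact the immunogenicity outcomes", and drops samples taken after a missed dose or a natural RSV infection. SAP 2.3.2.1 has the same two sample rules. Neither document names passive antibody or immunosuppressants.

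**Prohibited therapy.** Section 8 also says: "The sponsor must be notified in advance (or as soon as possible thereafter) of any instances in which prohibited therapies are administered". And: "If chronic use of prohibited therapies becomes medically indicated during the course of the study for any subject, the sponsor should be contacted". Section 17.1 has departures from the protocol reflected in the eCRF and source documents.

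**The concern.** The two toddler endpoints measured at Day 211 are RSV neutralizing and F-binding antibody. Immunoglobulin, blood products and RSV antibody products can carry antibody that these assays read. A child given one of them would then show a titre that is neither vaccine response nor background immunity.

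The plan already accepts this principle for natural infection, another source of RSV antibody unrelated to the vaccine: later samples leave the PPI set. Passive antibody contaminates in the same way but has no rule. After Day 57 the data needed to apply a rule are not collected either, and an analyst cannot recover what was never asked. Both arms are open to this, and the placebo arm is the smaller, so a single value weighs more there.

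**Working it through.** The documents give no figure for this point, so there is none to reproduce. The check sets the rules side by side and then does simple arithmetic.

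**1. Length of the gap.** Inputs: dose 2 at Day 29, end of the second 28-day window at Day 57, last immunogenicity sample at Day 211 (Protocol 3.1).
- 211 − 57 = 154 days, or 22 weeks.
- Share of the interval from dose 1: 154 / (211 − 1) = 73%.
- Share of the interval from dose 2: 154 / (211 − 29) = 85%.
- With visit windows of ±3 and ±14 days: shortest (211 − 14) − (57 + 3) = 137 days; longest (211 + 14) − (57 − 3) = 171 days.

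These days lack *routine, non-SAE* recording. SAE-linked therapy is recorded throughout.

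**2. What happens to a toddler given a licensed product of this kind, with no SAE.**

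| Timing | Breaks a written rule? | Recorded? | PPI rule? |
|---|---|---|---|
| After screening, before dose 1 | Yes: the note closing Section 4.2.2 requires exclusion if eligibility is lost | Yes, as pre-study therapy within 30 days before dose 1 | Not needed |
| Dose 1 to about Day 57 | No: criterion 33 looks back only and Section 8 is silent | Yes | None |
| About Day 57 to Day 211 | No | Not routinely | None |

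Section 4.3 binds subjects to the requirements in the entry criteria during the study, but criterion 33 contains no in-study requirement to carry forward. The sponsor notification in Section 8 applies to prohibited therapies, and these products are not listed as prohibited for toddlers.

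**3. Effect of one child on the geometric mean titre (GMT).** If one of n log titres is raised by a factor k and the others are unchanged, the GMT is multiplied by k^(1/n). Inputs: n = 24 active and n = 12 placebo (Protocol Table 5), taking everyone as contributing at Day 211. The value of k is an assumption; the documents give none.

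| k (assumed) | n = 24 | n = 12 |
|---|---|---|
| 4 | 1.059 | 1.122 |
| 8 | 1.091 | 1.189 |
| 16 | 1.122 | 1.260 |

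An 8-fold rise therefore shifts the GMT by about 9% in the active arm or 19% in the placebo arm. Over the range shown, the shifts are 6–12% and 12–26%.

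**The case against.** A reader might infer more than the documents support: that all therapy after Day 57 is lost, that immunosuppressed subjects sit unseen in the PPI set, or that a contaminated value could never be noticed. None of these holds.

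- **SAE-linked therapy is recorded to the end of the study.** Under Section 12.3.2 most hospitalizations are SAEs, so treatment associated with them is captured. Section 3.2 also collects drug treatments for RTI episodes, and the Cohort 1 calls in Section 9.1.4.3 ask about medical care sought. These give partial capture, but no contact asks about immunoglobulin, blood products or RSV antibody.
- **Prohibited immunosuppressants are notifiable at any time.** They count as departures under Section 17.1 and can leave the PPI set through the major-deviation clause. What remains is weaker: reporting is passive, and the pediatric sentence in Section 8 lacks a verb saying that the listed use is prohibited, so its force for unplanned in-study use is unclear.
- **Investigational antibodies are already barred.** Section 8 disallows experimental medication, and criterion 28 excludes joining another investigational study. Only licensed products fall through.
- **Exposure is likely rare.** Criteria 10, 23.1, 24 and 27 select healthy, term-born children without immunodeficiency or major anomalies. The documents support no exposure rate, and none is assumed here.
- **An odd value might be visible.** SAP 6.3.1.1 plots individual values and subject profiles. In placebo subjects a rise in F antibody can also be read as RSV infection (Protocol 2.1.2), after which samples leave the PPI set. But a plot does not show the cause, and removal as an infection would be right for the wrong reason and could miscount an exploratory endpoint.
- **The shift is small against sampling error.** If the SD of log2 titre is 1 to 2 (an assumption), the 95% CI limits lie a factor of about 1.3–1.8 from the GMT at n = 24 and 1.6–2.4 at n = 12. A 9% or 19% shift lies inside that.

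These points narrow the finding and limit its weight. They do not close the gap for licensed antibody-containing products in toddlers.

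**Conclusion.** The point holds in a narrow form. A licensed immunoglobulin, blood product or RSV antibody product given to a toddler after dose 1, without an SAE, is not a deviation under the current text and has no PPI rule. From about Day 57 to Day 211, 154 days, it is also not routinely recorded. The adult text differs from the toddler text here, and the documents do not explain why.

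The consequence is modest. Immunogenicity is a secondary, descriptive objective with no hypothesis test, toddlers give only humoral blood at Day 211, and exposure is probably uncommon. The 9% and 19% shifts rest on one exposed child, an assumed 8-fold rise and full arms of 24 and 12. They show scale and do not predict bias. The change is still worth making because it is cheap and follows a rule the plan already applies to natural infection.

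**What to change.** **Recording.** In Protocol Section 8, schedule note s, Visit 9 and the existing Cohort 1 calls, record through Day 211 any immunoglobulin, blood product or RSV antibody product, and any immunosuppressant use meeting the protocol's existing definitions, whether or not linked to an SAE.

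**Analysis.** In Protocol 11.1 and SAP 2.3.2.1, exclude from the PPI set samples taken after receipt of immunoglobulin, blood product or RSV antibody, in both arms and in the same way as for natural infection. Keep those samples in the Full Analysis tables. Leave immunosuppressants to the existing major-deviation clause. Dropping every sample after any short steroid course would go beyond the protocol's own restrictions and discard usable data from small arms.

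**Consistency.** The sponsor should reconcile the adult and toddler in-study passages (criterion 11, criterion 33 and the pediatric sentence in Section 8). Whether such treatment should be restricted is a clinical matter and is not proposed here.

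**Cost.** One targeted eCRF question at contacts that already take place, and one sentence in each analysis-set definition. An occasional Day 211 PPI value may be lost. For children already past Visit 9, the question can still be put at the remaining calls to one year, and the PPI sentence can be added before the final analysis.
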